Appendix 17: IBD-BOOST OPTIMISE Topic guides for all process evaluation interviews

Appendix 18: IBD-BOOST OPTIMISE Consent form for process evaluation interviews

1. BACKGROUND

Inflammatory Bowel Disease (IBD) affects 300,000 people in the UK (https://www.crohnsandcolitis.org.uk/about-inflammatory-bowel-disease), causing unpredictable bouts of gut inflammation, with acute illness, diarrhoea, and pain. In remission, many people with IBD live with fatigue, chronic pain, and bowel urgency/incontinence (1). There is no current cure for IBD, which usually starts in childhood or as a young adult. Most previous IBD research has focused on controlling inflammation. However, many people report continuing IBD-related fatigue (41%), abdominal pain (62%) and difficulty with continence (up to 75%) even when IBD is in remission (1-3). These symptoms limit peoples' quality of life and ability to work and socialise. Patients feel these symptoms are not taken seriously by health professionals and report that little help is given (4-6). However, the James Lind Alliance IBD research priority-setting consensus put fatigue, pain, and continence in the top 10 issues that IBD patients and clinicians want to be addressed by research (7).

1.1 The IBD-BOOST programme of research

The current application is stage three of IBD-BOOST, a National Institute of Health Research (NIHR) Programme Grant for Applied Research (PGfAR) funded programme. The overall aim of the Programme Grant is to improve the quality of life of people with IBD by reducing the burden of IBD-related fatigue, pain, and urgency/incontinence. See Appendix 1 (page 25) for an overview of the whole IBD BOOST programme.

The current protocol is for stage 3 of the programme, a non-randomised interventional study to test a checklist and algorithm for identifying and managing potential medical causes of these IBD-related symptoms.

Stage 1 of the programme involved focus groups and interviews with people with IBD and IBD nurses to inform the development of the checklist and algorithm under investigation in this study. This study was undertaken with REC Approval (REC reference: 17/WA/0349/IRAS number: 228902). Data from this stage has also been used to develop an online self-management intervention which will be hosted on an electronic platform.

Stage 2 of the programme involves a large cross-sectional survey to people with IBD to investigate the inter-relationships of these IBD-related symptoms and the proportions wanting support to manage these symptoms. This survey protocol has been approved by an Ethics committee (REC reference: 18/NW/0613/ IRAS number: 246185). Survey participants who consent to be contacted for further stages of our research, and who attend one of our clinical sites for their routine IBD care, will be invited to participate in the Optimise Study (this stage) and then, if eligible, will later be invited to participate in the RCT.

Stage 3 (this project) of the programme is a non-randomised interventional study to test a checklist and clinical management algorithm which we have developed within this programme for identifying and managing the most common medical causes of these IBD-related symptoms. We will then address any medical abnormalities detected. Participants who have no medical causes identified by the checklist and algorithm, or who have abnormalities and complete this medical optimisation but have continuing symptoms after medical optimisation will then be invited to take part in an RCT of online self-management. The RCT will also be offered to eligible people declining participation in the present study, or who consent to the present study and complete the checklist but who subsequently decline any suggested medical test or intervention.

Stage 4 is a Randomised Controlled Trial (RCT) of online self-management for these symptoms, with an embedded pilot study, a study within a trial, a health economics evaluation and process evaluation. Potential participants will already have completed the stage 2 and possibly stage 3 of the IBD-BOOST programme of studies.

1.2 Rationale

These symptoms of fatigue, pain and urgency/incontinence have a major impact on quality of life in people with IBD, but have been largely ignored by clinicians and researchers. Our programme, shaped by the concerns of our patient and clinician stakeholders, focuses on a supported online self-management intervention for these symptoms. The checklist and algorithm stage (this study) will help identify participants who will be suitable for a self-management intervention and ensure that anyone displaying "red-flag" symptoms (indicating an urgent or serious medical issue) is identified for prompt treatment. It is currently unclear how useful it is to investigate these symptoms and whether symptoms will respond to correcting biomedical abnormalities.

1.3 The need for research

It is currently unclear how best to manage these common symptoms of fatigue, pain and urgency/incontinence in people with inflammatory bowel disease. Many patients do not report these symptoms at all, or if they do are offered little beyond investigation and treatment of active disease. We have found in previous work that many patients do not receive what are considered "standard care" investigations or management for these symptoms (8).

Our previous systematic literature reviews (9-12) have identified many potentially reversible causes for these symptoms. Many of these, particularly the psycho-social elements, will be addressed in our online self-management programme which follows on from the current proposal within our programme grant. However, there are also "medical" causes (such as anaemia as a cause of fatigue), which could be addressed before patients enter a self-management programme. However, during extensive consultation with expert clinicians during development of the current checklist and algorithm, there is genuine equipoise over whether patients need these medical causes addressing, whether it is likely to make any difference to symptoms, or whether they should be able to directly access online self-management (the RCT in the next stage of our programme).

1.4 Development of the checklist and algorithm

Our development work for this study has involved consulting a wide variety of gastroenterologists, IBD specialist nurses, patients and others. This work suggests that there is no current "standard of care" for investigating and treating these symptoms. Some clinics do very little while others conduct many different tests, with little consideration of costs or inconvenience to patients.

Over an extensive series of interviews and group activities with stakeholders, we have now developed consensus on the contents of an algorithm for investigating and managing symptoms of fatigue pain and urgency/incontinence, with an accompanying preliminary self-completed checklist. During this development we have focussed on the common evidence-based causes (from our systematic reviews above) and interventions for our three symptoms (fatigue, pain, urgency), which consultees felt were also feasible for implementation in routine clinical practice. We have tried to achieve a balance between feasibility, costs and

completeness. There were many other candidate tests, which were either not evidencebased or that patients and clinicians felt were too onerous to be part of routine clinical care for all patients with these symptoms.

The IBD-BOOST Algorithm (Appendix 3) and preceding patient-completed Checklist (Appendix 4) are a pragmatic algorithm for detecting and treating the most likely/common causes for symptoms (based on the evidence base in the literature reviews above). It is intended to be suitable and feasible for implementation by IBD nurse specialists or other IBD clinicians (or GPs outside of this study) in their routine everyday practice. It therefore consists of "red flags" (the clinical conditions that are considered essential to know and that would potentially make self-management dangerous), and disease activity via a simple test (faecal calprotectin) and a self-report questionnaire (IBD-Control)(13). If there are no red flags and IBD is apparently in remission, only the most common evidence-based causes for symptoms of fatigue, pain and urgency considered essential by clinicians and patients during our development work, are then explored. Nurses and other clinicians who will implement the algorithm at our clinical sites will receive a face to face or online training session and a training manual for reference on how to use the checklist and algorithm.

The nurse/clinician will initially review the patient's responses to the checklist, the result of a faecal calprotectin test and the medical notes and decide if the patient is clearly in remission and has no "red flags" or other issues which need investigating, according to the algorithm. Some participants will at this point clearly have no need for further action and be eligible for entry into the RCT for self-management (separate to the current application). Others will need a follow up phone call to clarify some issues, or need a face to face review with the nurse/clinician, or immediate onward referral to medical colleagues (if they have "red flags" which warrant urgent medical attention).

Depending what these enquires reveal, the nurse will then initiate appropriate management for any abnormalities found which may be causing symptoms (such as active IBD disease or anaemia). If tests or new management are initiated, the nurse will determine, using clinical judgement, whether to see the patient face to face or follow up via telephone or email. S/he will review the patient or the results of tests as necessary and decide when the patient's symptoms have been "optimised", over the following 3 months, while recognising that in IBD not all biomedical abnormalities and disease activity may be resolvable. The management initiated will be standard care treatments (as agreed during our consensus process) and not any novel interventions outside of standard care. Tests ordered, their results and management initiated will be recorded after each activity on a study Case Report Form (CRF) (Appendix 5; IBD-BOOST Medical Management Optimisation CRF).

2. OBJECTIVES

2.1 Primary research question:

I. Of those people with IBD who experience fatigue, pain and/or faecal urgency/incontinence and express an interest in intervention for one or more of these symptoms, what proportion have patho-physiological contributors which are potentially medically treatable?

2.2 Secondary research questions:

- I. Is implementing this checklist and algorithm feasible in routine NHS clinical practice?
- II. In patients with symptoms and potentially reversible medical causes do these symptoms change at 3 months after initiating algorithm-led management? Note: the design of this study will not allow inference of causality of symptoms.
- III. In patients starting algorithm-led management, what NHS resources are used during the implementation of the algorithm?
- IV. In patients starting algorithm-led management, what change is observed in healthrelated quality of life (EQ 5D 5L utility)?
- V. What is the experience of nurses implementing the Optimise algorithm and what are their suggestions for any changes to enable future NHS implementation (via qualitative interviews)?

This study also aims to identify and prepare potential participants for a future RCT of an online symptom management intervention. Participants who are not found to have any potentially treatable patho-physiological contributors will be invited to take part in the next stage of the programme, an RCT of an online self-management intervention. Participants who are identified as having potentially treatable contributors but have not experienced resolution of symptoms after three months of following the algorithm and want further help with symptoms will also be invited to the RCT.

3. STUDY DESIGN

This is a non-randomised interventional study to identify and prepare participants for the subsequent RCT which will follow. Potential participants will have already been identified via a survey in stage 2 (REC reference: 18/NW/0613/ IRAS number: 246185), as having symptoms and wanting help for them, as well as receiving their routine IBD care from one of our participating NHS trusts.

Those participants expressing a desire for help with symptoms and giving permission for future research contact when completing the survey will be sent a link to an online version of the checklist (Appendix 4) with up to 2 reminders by email or text message for non-responders. Alternatively, the checklist can be sent by post, the participant will receive a letter with information sheet, consent form, checklist and stamped addressed envelope. The checklist will be self-completed by the participant. The checklist also has a section measuring symptom severity and IBD control using validated measures. Participants consenting to the study and returning a completed checklist will then be sent a kit for a postal stool sample for faecal calprotectin to be sent to a central laboratory. This is to detect active IBD disease and forms a step in the algorithm for assessment of active disease.

The central team will alert clinical sites when one of their patients completes the checklist and faecal calprotectin test (permission for this is outlined in the participant information sheet and consent form). The checklist will be sent to the clinical team within 10 working days of the central study team receiving the completed checklist. An IBD nurse or other member of the clinical team (trained in using the checklist and algorithm) at the corresponding NHS site will then review the checklist and result of the faecal calprotectin test for any red flags and potentially reversible causes with reference to the algorithm (Appendix 3). A telephone call or clinic visit may be used for clarification of any unclear element.

If nothing further needs to be done according to the algorithm (patient is in remission and no further tests or management is indicated), the participant will be informed of this, thanked for their participation by letter/email (Appendix 14). They will be offered the RCT if they have consented for further research contact and are eligible for the RCT. If active IBD disease or any other of the issues in the IBD-BOOST algorithm are identified, the IBD nurse/clinician will initiate management based on the algorithm.

If a participant is clinically unwell, with a plan to change their IBD management at the time of their checklist being reviewed, their study participation should be paused. The participant should be informed of this pause in their participation via email/letter (Appendix 15) and a new checklist should be re-sent to them 6 months later via post or email. This new checklist should then be used to follow the algorithm. Participants will also complete a new faecal calprotectin sample at the same time as completing the new checklist.

Participants will have completed measures of symptom severity and IBD control when completing the checklist. If intervention is indicted by the algorithm, they will complete the patient reported outcome questionnaire (Appendix 6) at 3 months after return of both the checklist and faecal calprotectin test (only for those for whom the checklist indicates an abnormality which the algorithm addresses). Nurses will keep a record of their interactions with patients (phone calls, emails or clinic visits), tests ordered, results and interventions using a case report form (Appendix 5).

4. STUDY POPULATION

Adults with IBD who have completed the IBD-BOOST survey at stage 2 of our Programme Grant (REC reference: 18/NW/0613/ IRAS number: 246185) and have indicated on that survey that they would like further support for their symptoms. Those completing the survey who consented to being contacted for further research will be invited. The previous survey includes diagnosis, age, current country of residence, symptom scores and whether they would like further support. From this, the central research team will be able to ascertain who is eligible to be invited to participate in Optimise from participating clinical sites.

4.1 Inclusion criteria

- Diagnosis of IBD (including patients with an ileo-anal pouch or stoma)
- 18 years and over
- Lives in UK and attends one of the IBD-BOOST NHS clinical sites for routine IBD care
- Has completed the IBD-BOOST survey (stage 2) and indicated that they would like further support to help manage their symptoms
- Ability to give informed consent and sufficient command of English to understand study documents and procedures will be assumed from response to previous survey

4.2 Exclusion criteria

• Under 18 years

4.3 Sample size

From the prevalence of symptoms, we anticipated that at least 50% of 6,300 predicted respondents to the survey (stage 2) would report one or more symptoms of fatigue, pain or

urgency/faecal incontinence (n=3,150 symptomatic people). Of these, we anticipated approximately one third expressing an interest in further management for symptoms and attending one of our clinical sites for their routine IBD care, so approximately 1,000 people available as potential recruits for the present study. Of these, we anticipated 50% (500) would consent to recruitment to the present study. However, as a result of the impact of the Covid-19 pandemic on recruitment we have needed to reduce our overall sample size target from 500 to 200 participants, and the study will now focus on checklist and algorithm feasibility and descriptive statistics. With this sample size the width of the 95% confidence interval (CI) for the proportion of participants who have patho-physiological contributors which are potentially medically treatable would be at most 13.9% (normal approximation CI).

4.4 Identifying and Recruiting Participants

Potential eligible participants will be identified by the central study team, based on responses to the previous Ethics-approved survey indicating presence of symptoms and desire for intervention. Survey respondents who are receiving clinical care at one of our study clinical sites will be identified by the central team (if they have given consent for future contact). For the purposes of eligibility for the Optimise study, a completed survey (previous study) will be defined as having the following fields completed (number relate to previous survey items):

- Part 1: contact details
 - 1. First Name
 - 2. Surname
 - 3. Phone number
 - 4. Email address
 - 5. Postal address (required for calprotectin, and to check UK residence)
 - 11. NHS site
- Part 2: your IBD and your health
 - 1. Which of the following have you been diagnosed with?
 - a) Crohn's disease
 - b) Ulcerative Colitis
 - c) Other form of inflammatory bowel disease
- Part 3 Symptoms;
 - a. At least one section (Pain, Fatigue or Urgency) complete.
- Part 8
 - 1. Gender
 - 2. Age in years
 - 3. Ethnicity

Potential Optimise participants will be sent a Participant Information Sheet (PIS) (Appendix 7) and will consent to the current study either via a link emailed or via a paper consent form posted to them by the central team (Appendix 8 for invite email: one reminder if no response is received; Appendix 9 (consent form paper copy/online copy). Those consenting will then receive a subsequent link to the online checklist. If consenting via post a paper copy of the checklist will be sent with the PIS and consent form. There will be two reminders by email or text for those consenting but not returning the checklist after one and three weeks (see Appendix 10).

Responders completing the checklist will receive a postal kit for a stool sample, to be posted to a central laboratory for analysis of faecal calprotectin levels as an indicator of disease

activity. There will be two reminders by email or text for those receiving a stool sample kit but not returning it at 2 weeks and 4 weeks after being sent (Appendix 10).

Checklists will be sent to the sites teams once completed in order for the clinical team to act on any responses to the checklist which may require urgent attention. Once the calprotectin results are received, the central team will again notify the relevant clinical site for that participant and pass on the faecal calprotectin test results for clinical review using the algorithm. This transfer of personal data is clearly outlined in the PIS and consent for this is included on the consent form. A copy of their calprotectin results will be emailed to participants from a secure NHS email address along with an explanation that it will be passed on to their care team: (Appendix 12).

5. CONSENTING

Written information about the study (Appendix 7) will be emailed or posted to potential participants. Participants will be able to participate by providing consent via a paper consent form (Appendix 9) or via an online link (Appendix 8) emailed to them by the central team.

The right of the participant to refuse to participate without giving reasons will be respected. All participants are free to withdraw from the study at any time without giving reasons and without prejudicing further treatment. Their right and access to their usual NHS treatment will not be compromised in any way if they do decline to participate or withdraw. In line with GDPR guidelines, participant rights to access, change or move their information will be limited, as we will need to manage information in specific ways in order for the research to be reliable and accurate. If a participant chooses to withdraw from the study, we will keep the information that we have already obtained and no further information or data will be collected. To safeguard participant rights, we will use the minimum personally-identifiable information possible. All study participants will notify the Chief Investigator and lead research team based at King's College London if they wish to withdraw, using the contact details provided in the patient information sheet for the study.

[figure not shown]
6. DATA COLLECTION

The checklist (Appendix 4) and outcome measures at 3 months (Appendix 6) will be selfadministered. Participants will be invited to complete these through an online link provided or via paper copies sent to the study research team and stored at King's College London or LNWUH Trust. Data from the online version will be directly inputted into the database by participants. Paper copies received in the post will be inputted manually into the database by the research team.

Results for calprotectin tests on stool samples provided by the participant will be accessed by the central research team on King's College Hospital laboratory's secure results portal and uploaded on to the study database on the Calprotectin CRF (Appendix 11). Once the checklist and algorithm data are both available the participant's usual care clinical site will have four weeks to review and contact the participant.

If the checklist indicates an abnormality which the algorithm addresses, the participant will be sent the patient reported outcomes questionnaire (Appendix 6) at 3 months after the IBD nurse has reviewed the checklist. The questionnaire contains measures on symptom and IBD control repeated from the checklist and measures of quality of life also used in the IBD-

BOOST survey. Those who require a 3 month follow up will be sent this via email/letter and will be sent up to 2 reminders by email or text message for non-responders (Appendix 10).

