6.2 Outcome measures

Primary outcome measures

Proportion of participants with any of the following detected via the checklist, faecal calprotectin test or by the nurse/clinician following the algorithm (recorded on the Checklist, Appendix 4 & Optimisation CRF, Appendix 5):

- "Red flags" on checklist which require investigation
- Active disease (defined as faecal calprotectin 200 or over and/or IBD control score 13 or under)
- Abnormalities detected on blood test in people with fatigue
- Irritable Bowel Syndrome or functional dyspepsia diagnosed in people with pain (by responses on checklist)
- Untreated loose stool detected in people with urgency

Secondary outcomes

- Proportion of participants for whom a clinical intervention was indicated
- Proportion of participants who declined a suggested clinical intervention at consultation
- The cost of implementing the algorithm (clinical tests or intervention and nurse/clinician time to implement the algorithm)
 The checklist (Appendix 4) also includes the following measures, which will be repeated at 3 months (Appendix 6):

- PROMIS Short Form v1.0 Fatigue 4a; 4 item validated scale to measure fatigue (14)
- PROMIS Scale v1.0 Pain Intensity 3a; 3 item validated scale to measure pain (14)
- PROMIS Scale v1.0 Gastrointestinal Bowel Incontinence 4a; 4 item validated scale to measure bowel control (15)
- IBD-Control score; 8-item self-reported score to measure disease control from the patient's perspective (13)
- EQ-5D-5L (Quality of Life measurement); a 5-item standardised measure of health (16)

Only those participants needing interventions as indicated by the algorithm, will be sent the outcome questionnaire (Appendix 6) at 3 months after return of the initial checklist and stool sample. This questionnaire will also include a free text feedback option at follow up to capture qualitative comments about the experience of completing the checklist and algorithm, and how onerous or helpful this was.

In addition, the nurse/clinician will complete the Optimisation CRF for each participant (Appendix 5), this will include number of visits or telephone contacts, all tests and results and all management initiated within the algorithm. Qualitative comments on taking the participant through the process of using the checklist and algorithm will be collected here.

Feasibility outcomes will include number consenting but then discontinuing (with reasons if possible), completion of outcome measures, completion of CRFs.

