6.3 IBD-BOOST Study Schedule

IBD-BOOST OPTIMISE		Within 1 week of completing checklist	Within 10 weeks of consent/ 2 weeks of trial team receiving the calprotectin result	Within 4 weeks of checklist and calprotectin data sent to clinical team	Within 3 months of checklist and calprotectin result reviewed	3 months after checklist and calprotectin result reviewed	Before study closure
Time Point	Т0	T1	T2	Т3	T4	T5	T6
Screening and invite sent	Х						
Participant Information Sheet	Х						
Consent Form	Х						
Checklist	Х						
Stool sample kit sent to participant		Х					
Calprotectin result received and uploaded by central research team			X				
Checklist and calprotectin result reviewed by patient's local IBD team				Х			
Medical Management Optimisation (if required)					X		
Participant reported Outcome Questionnaire completed (only if management provided)						X	
Clinician Qualitative Process Evaluation Interviews							Х

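### The 3-month questionnaire is dated from sample return in sections 3 and 6.2 but from site review in section 6 and schedule T5; the review trigger is misworded, and no rule is given for an unreturned stool kit

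*Protocol*

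**What the plan says.** Four places date the questionnaire sent to participants who need management:

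- Section 3: "at 3 months after return of both the checklist and faecal calprotectin test".
- Section 6.2: "at 3 months after return of the initial checklist and stool sample".
- Section 6: "at 3 months after the IBD nurse has reviewed the checklist".
- Section 6.3, T5: "3 months after checklist and calprotectin result reviewed".

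The steps before it are set out in the schedule. The calprotectin result is uploaded at T2, "Within 10 weeks of consent/ 2 weeks of trial team receiving the calprotectin result". The site reviews at T3, "Within 4 weeks of checklist and calprotectin data sent to clinical team". T4 then allows up to 3 months from that review for medical optimisation. Section 6 describes the same four-week site window but opens it with "Once the checklist and algorithm data are both available".

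The checklist itself goes to the site early, "within 10 working days of the central study team receiving the completed checklist" (section 3). Section 4.4 gives the purpose, which is to let the site act on urgent answers, and places the review under the algorithm after the calprotectin result has been passed on. Section 4.4 also provides kit reminders at 2 and 4 weeks. It does not say what happens if the sample still does not come.

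**The concern.** Research question II (section 2.2) asks how symptoms have changed 3 months after management under the algorithm begins. Management begins at or after the site's review, except where an urgent checklist answer has already been acted on. A questionnaire dated from return of the sample therefore reaches people before they have had 3 months of management, and how far before depends on how long the laboratory and the site took. If some staff follow section 3 or 6.2 and others section 6 or the schedule, the change scores for fatigue, pain, incontinence and EQ-5D-5L mix different exposure times under one label.

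The wording of the review trigger raises a second, smaller matter. Section 6 makes the start of the review depend on data that the review itself produces. Read as intended, it depends on calprotectin, and then a participant who returns the checklist but no sample has nothing to start the full review.

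**Working it through.** The protocol states no figure for the gap between the two start points, so there is none to reproduce.

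**Step 1. Type of start point.**

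| Place | Event counted from |
|---|---|
| Section 3 | Return of checklist and sample |
| Section 6.2 | Return of checklist and sample |
| Section 6 | Nurse's review |
| Section 6.3, T5 | Review of checklist and calprotectin result |

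Two places use return and two use review.

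**Step 2. Size of the gap.** Inputs:

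- 3 months = 3 × 365.25 / 12 / 7 = 13.04 weeks.
- Site window: 4 weeks (section 6 and T3).
- Laboratory time: not stated. The 3-week limit in section 6.4 for emailing the participant a copy of the result is used as a stand-in.
- Upload: 2 weeks (T2).

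Adding these limits is an assumption, because the protocol gives no total. With lag L from return to review, the review rule puts the questionnaire 13.04 + L weeks after return. The return rule puts it 13.04 − L weeks after review.

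| Lag L | Review rule: weeks after return | In months | Return rule: weeks after review |
|---|---|---|---|
| 4 (site window only) | 17.0 | 3.92 | 9.0 |
| 4 + 3 = 7 | 20.0 | 4.61 | 6.0 |
| 4 + 3 + 2 = 9 | 22.0 | 5.07 | 4.0 |

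Under the return rule the questionnaire comes L weeks before the T4 window closes: 4 weeks before in the mildest row and 9 weeks before in the last. Sites that review faster have a smaller gap.

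**Step 3. The trigger.** Sections 3 and 4.4 have the site apply the algorithm during its review, so algorithm data cannot exist beforehand. The sentence just before the trigger in section 6 concerns calprotectin results, and T3 names calprotectin data. The word should be calprotectin.

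**Step 4. A participant with no sample.** With the trigger corrected, the four-week review in section 6 waits for calprotectin. So do the review in section 4.4, T3 and T5. The return dates in sections 3 and 6.2 also never arise. Yet section 6.2 lets the checklist alone meet three of the five parts of the primary outcome: a red flag, active disease through IBD-Control of 13 or under, and irritable bowel syndrome or functional dyspepsia by checklist responses. Such a person can be a primary-outcome case who needs management and still have no date for full review or follow-up.

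**The case against.** The best defence of the return rule is that the symptom baseline is taken on the checklist, so counting from return keeps the time since baseline more even. That is true as far as it goes. But the return rule also waits for the stool sample, so it does not fix that interval either, and research question II is framed from the start of management. Section 7.1 likewise evaluates EQ-5D-5L change to the end of optimisation, which the return rule can precede.

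Three stronger readings are tempting, and the documents do not support them.

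- *That section 6 would follow up a participant with no sample while the other sections would not.* This takes the section 6 phrase about reviewing the checklist in isolation. Section 3 has the nurse review the checklist together with the calprotectin result, and section 4.4 ties algorithm review to that result. For these participants the sections do not disagree; a rule is absent. The algorithm, CRFs and training manual are not shown and could supply one.
- *That urgent problems go unseen without a sample.* Section 4.4 covers urgent answers ahead of the result.
- *That non-returners are lost to the primary estimate and widen its confidence interval.* The protocol gives no return rate, many non-returners could be classified from the checklist, and the handling of missing calprotectin is commonly left to the SAP.

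**Conclusion.** The conflict between return and review is real and lies within the protocol's own text, so no unseen appendix or SAP removes it. It affects everyone followed up. The gap is up to about 4 weeks from the site window alone, and about 7 to 9 weeks if the laboratory and upload limits are added in full, which is an assumption. The return rule is the one to drop, because it does not fit research question II or the T4 window. The trigger in section 6 is a plain wording slip. The missing rule for an unreturned kit is secondary, and the number affected cannot be estimated from the protocol. Overall the point is minor: the study is descriptive and rules out causal inference, and short edits settle the matter.

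**What to change.** 1. In sections 3 and 6.2, count the 3 months from the site's review in place of return of the two items, to match section 6 and T5.
2. In section 6, replace the reference to algorithm data with the calprotectin result, to match T3.
3. Secondary: after the kit reminders in section 4.4, add a rule such as *If no sample has arrived 6 weeks after the kit was posted, the site reviews the checklist and notes without it, calprotectin is recorded as not done, and the 3 months run from that review.* The 6 weeks is a suggestion (2 weeks after the second reminder); any set time would serve.

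**Cost.** One amendment with sponsor authorisation and REC and HRA approval (section 8.2), and a *not done* entry for calprotectin on the CRF if there is none. Sites take on the review of non-returners. Relative to sections 3 and 6.2 the questionnaire goes out some weeks later, so anyone reviewed after 31 December 2022 would fall due after the planned follow-up end of 31 March 2023. For a non-returner, review could come up to 1 + 6 + 4 = 11 weeks after the checklist (kit sent within 1 week at T1, 6-week wait, 4-week review), so checklists completed in the last 11 weeks of recruitment could be affected. The follow-up end date may need a short extension. The review start point is also not exactly the start of management, since tests can delay treatment, but it is closer than return.
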